5 STUDY OBJECTIVES

5.1 PRIMARY

The primary objective of this study is to evaluate the effect of virtual approach via novel technologies versus traditional study conduct on glycemic control in terms of HbA1c.

5.2 SECONDARY

The study secondary objective is to evaluate the appropriate utilization of virtual approach via novel technologies during the study and to assess the effect of the virtual versus traditional study conduct on multiple outcomes in terms of study methodology and diabetes control:

- Study methodology with the two approaches:
 - Patient satisfaction with the trial experience via a PRO
 - Impact of clinical trial participation via a PRO
 - Patient burden with the clinical trial experience via a PRO
 - Resource use via a PRO
 - Medication and key study activity compliance
 - Patient retention
- Diabetes control with the two approaches:
 - Diabetes related PROs
 - Glycemic control (HbA1c, FPG, SMPG)
- Patient care with the two approaches:
 - Doctor/site-patient relationship
 - Site satisfaction with provisioned care
 - Patient experience in the clinical trial via a qualitative exit interview
- Safety assessment managed by the two approaches including:
 - Hypoglycemic events
 - Adverse Events (AEs)

6 STUDY DESIGN

6.1 DESCRIPTION OF THE STUDY

MSC15146 (eStudy) is a randomized, open label, 2 approach groups, multicenter pilot study. The study is a postmarketing Phase 4 trial which will recruit outpatients with Type 1 diabetes mellitus (T1DM) currently treated with insulin glargine 100 U/mL (eg, Lantus or Basaglar) plus rapid-acting insulin analogs. The patients must have access to mobile technology (eg, smartphone) and be digital-literate. They will eSign the consent on the study website.

The study will be conducted in the US and in Canada with at least 3 participating investigational centers. It is planned to recruit 150 patients.

Eligible patients will be randomized 1:1 (virtual : traditional) into 2 study groups to follow one of two approaches for completion of all study procedures:

- a remote, virtual approach (n = 75 patients); patients of this group will not visit the study sites during the entire study course, except for a physical examination before IMP initiation. All study assessments, including vital signs, weight, lab variables, etc, will be completed via the Bluetooth devices that instantly transfer the digital data, available for investigators' view. Video chat between the patients and investigators/designees may occur for safety reason in addition to the planned study visits.
- a traditional trial approach (n = 75 patients)

Stratification factors for randomization include study site and HbA1c <7.6% or ≥7.6%. The rationale for stratification by study site is the small number of sites and the fact that some assessments for patient care are done at site level. It is therefore deemed important to ensure balance at site level in number of patients randomized across the virtual and traditional approach groups. Patients of both groups will receive the same IMP: daily subcutaneous (SC) injection of Toujeo as the basal insulin. Protocol-mandated background therapy consists of the existing rapid acting insulin analogs (Humalog, Novolog, or Apidra) that have been used before the start of the study and will be continued throughout the study. This background treatment will not be supplied by the sponsor.

The study consists of 3 periods:

- an up-to-3 week screening period
- a 24-week treatment period
- a 1-week post-treatment period (follow-up)

The **screening period** includes 2 steps to complete the digital consent process via the study-specific webpage and the eligibility assessment by the study site. Screening procedures will be performed by Homecare services (via the Medical Research Network [MRN]) provided medical professional in collaboration with the investigators. The investigators will then complete the

eligibility assessments at the end of screening, the randomization, and the shipment of study material (Step 2).

During the 24-week **treatment period**, the patients in both groups will receive the same study treatment with Toujeo as the basal insulin plus their existing rapid-acting mealtime insulin analogs (Humalog, Novolog, or Apidra) to manage their diabetes. Toujeo dose will be titrated to target the fasting SMPG between 80 and 130 mg/dL; meal time insulin analogs will be adjusted following investigators' instructions to maintain postprandial SMPG within a range of 130 to 180 mg/dL.

All patients will monitor their plasma glucose via the study provided glucose meter. The SMPG values will be used to guide the insulin dose adjustment and document the hyper- or hypoglycemic events.

Any posttreatment safety information will be collected during the 1-week **posttreatment period**.

6.2 DURATION OF STUDY PARTICIPATION

6.2.1 Duration of study participation for each patient

The study duration consists of:

- An up-to-3 weeks screening period. The screening starts from signed consent form
- A 24-week treatment period
- A 1-week (+/-2 days) posttreatment safety follow-up after treatment completion or premature discontinuation of study treatment.

For an individual patient, the maximum study duration is about 28 weeks.

6.2.2 Determination of end of clinical trial (all patients)

End of clinical trial is defined as the last patient completes the last visit (Visit 13).

6.3 INTERIM ANALYSIS

No interim analysis

7 SELECTION OF PATIENTS

7.1 INCLUSION CRITERIA

- I 01. Patients with T1DM diagnosed at least one year before the screening visit
- I 02. Patients who are treated with multi-dose insulin using insulin glargine 100 U/mL (eg, Lantus or Basaglar) as basal insulin and rapid- acting insulin analogues as bolus insulin
- I 03. Patient with access to or experience with mobile technology (eg, tablet or smartphone)
- I 04. eSign the consent on the study web portal

7.2 EXCLUSION CRITERIA

Patients who have met all the above inclusion criteria listed in [Section 7.1](#) will be screened for the following exclusion criteria which are sorted and numbered in the following 2 subsections:

7.2.1 Exclusion criteria related to study methodology

- E 01. Age <18 years at screening (Visit 1 – Step 1)
- E 02. Type 2 diabetes mellitus
- E 03. HbA1c <5.4% or \geq 9.0% measured at screening (Visit 1- Step 2)
- E 04. Patients who received less than 6 months treatment with any basal plus mealtime insulin
- E 05. Use of any basal insulins other than insulin glargine 100 U/mL (eg, Lantus or Basaglar) within 3 months before screening
- E 06. Use of an insulin pump within 6 month before screening
- E 07. Use of meal-time insulin other than rapid-acting insulin analogs (Humalog, Novolog, or Apidra), eg, human regular insulin, within 30 days before screening
- E 08. Use of any noninsulin injectable or oral antidiabetic medication within the past 3 months before screening
- E 09. Use of systemic glucocorticoids (excluding topical application or inhaled forms) for one week or more within 3 months before screening
- E 10. Use of any investigational drug(s) within 3 months, or 5 half-lives, whichever is longer, before screening (Visit 1)

- E 11. Patients with severe systemic disease or with short life expectancy or any medical condition that might interfere with the evaluation of study medication according to investigator's medical judgment
- E 12. Hemoglobinopathy resulting in undetectable HbA1c by the central laboratory, or hemolytic anemia requiring transfusion of blood or plasma products within 3 months before screening
- E 13. Mental disorders or any neurologic disorder that would affect patient's ability to meet the study requirements, or patients deemed unlikely to safely manage insulin dosage by the investigator
- E 14. Patients with insufficient smartphone skills or unwilling to properly use the virtual tools deemed by the investigator based on the observation over the digital screening procedure
- E 15. Patients unable to speak, read, or write
- E 16. Patient is the investigator or any subinvestigator, research assistant, pharmacist, study coordinator, other staff or relative thereof directly involved in the conduct of the protocol.

7.2.2 Exclusion criteria related to the current knowledge of Sanofi compound

- E 17. Known hypersensitivity/intolerance to insulin glargine, rapid-acting insulin analogs, or any of their excipients
- E 18. Patients experienced with any severe hypoglycemic episode resulting in seizure, unconsciousness, or coma, and/or leading to hospitalization during the past 6 months before screening
- E 19. Documented (within 12 months) medical history of unstable proliferative diabetic retinopathy or or macular edema likely to require laser, surgical treatment during the study period
- E 20. Pregnant or breast-feeding women or women who intend to become pregnant during the study period
- E 21. Woman of child-bearing potential (WOCBP) not protected by highly-effective method(s) of birth control and/or who are unwilling or unable to be tested for pregnancy (see contraceptive guidance in [Appendix A](#)).
- E 22. Any country-related specific regulation that would prevent the subject from entering the study

Note: A patient should not be randomized more than once. One time re-screening is allowed at the Investigator's medical judgment for any manageable reasons that cause the screening failure and the patient is likely to be eligible before the enrolment completion.

8 STUDY TREATMENTS

8.1 INVESTIGATIONAL MEDICINAL PRODUCT(S)

The IMP is Toujeo (insulin glargine 300 U/mL, HOE901-U300).

Note: Dilution or mixing of Toujeo with other insulins is not allowed.

8.1.1 Formulation

Toujeo (HOE901-U300) is supplied for SC injection as a sterile, nonpyrogenic, clear, colorless solution in the Toujeo SoloSTAR® pen (a prefilled, disposable pen for insulin glargine 300 U/mL).

Each pen contains in total 450 units of insulin glargine (1.5 mL of 300 units/mL insulin glargine solution). This pen allows dose setting in the range of 1 to 80 units with a minimum of 1 unit increment.

8.1.2 Injection devices and training for injection devices

8.1.2.1 Injection devices

Patients will be provided with needles and the pen injection devices (prefilled study drug pens) specifically labeled for the use in the study.

The following commercial pen needles will be provided for use with the disposable injection pen devices:

- BD Ultra Fine Needles 31 G x 5 mm
- BD Ultra Fine Needles 31 G x 8 mm

Handling procedures of the pen and needles and administration technique is provided in specific manuals. The patients will be reminded of the IMP dosage at Visit 2-Step 2 before the IMP administration. For the duration of the treatment, the patients will be required to use the same type of study drug disposable pens and needles.

Pen device issues (malfunctions) should be reported to the sponsor by the means of a procedure on product technical complaint (PTC) forms (see details in [Section 8.1.2.4](#)).

Injection pens should never be shared with others.

8.1.2.2 Injection pen for Toujeo

All study patients will receive the appropriate number of disposable pens for Toujeo (insulin glargine 300 U/mL) and needles according to the dose range.

Each pen contains a cartridge with a total 450 units of insulin glargine. Doses can be set in steps of 1 unit. If a dose of Toujeo greater than 80 units is required, it will be given as two or more consecutive SC injections at the same time with the daily dose split in equal or close to equal doses. Splitting the doses into a morning and evening injection is not allowed.

8.1.2.3 Training on injection devices

Instructions for use will be provided, which explain how to use the disposable pen injectors. The injection device for the IMP is the same as or similar to the device that they have used for insulin glargine 100 U/mL. Therefore, no additional training on the devices is planned. The capability of self-injection with the SoloSTAR pen will be checked by the site staff in-person (traditional group) or via video technology (virtual group).

8.1.2.4 Pen-related events

A Pen-Related Event (PRE) includes any suspected problem with the injection device(s) used in the study which has or may lead to a health hazard (eg, AE). Typical problems include pen performance failure, patient (or caregiver) having difficulty understanding the instructions or using the pen, use error, etc.

Examples of PREs include but are not limited to:

- Dosing problems: jamming, inability to inject, partial injection, need to repeat injection, dosage knob stuck
- Needle issues: difficulty attaching the needle
- Breakage of the pen
- Difficulty to understand the instructions in the instructions for use
- Use error: Incorrect use of the pen by the patient/caregiver/healthcare provider

Pen-related events will be proactively monitored during the study by asking at each study visit whether the patient/caregiver experienced any PRE. If answer is yes, the specific electronic case report form (e-CRF) PRE Questionnaire will be completed.

If the PRE is associated with a symptomatic hypoglycemic event, a hyperglycemic AE or another AE, the corresponding symptomatic hypoglycemic forms or AE forms must also be completed. This associated AE will be qualified as a serious adverse event (SAE) only if it fulfills seriousness criteria, and in this case, the SAE reporting procedure ([Section 10.4.3](#)) should be followed.

As needed, further instruction and troubleshooting guidance should be provided to the patient by the study site according to the instructional materials/troubleshooting guide provided by the Sponsor.

For PREs that are not resolved by further guidance/review of instructions or troubleshooting with the pen during a visit, a PTC form must be completed, the pen associated with the event should be retrieved and both should be sent to the manufacturing site for technical investigation.

8.1.3 Provision of investigational medicinal product

Patients of the traditional group will be provided with the IMP by the site pharmacist or investigator during the on-site visits (Visit 2-Step 2, Visit 6, Visit 8, and Visit 10).

Patients of the virtual group will receive the IMP at home using the Direct-To-Patient (DTP) service. Patient identification remains confidential and will not be disclosed to study sponsor. For this reason, the IMP delivery will be managed by the Marken company (service provider). The clinical site will advise the patient as appropriate as to how the DTP process operates before the DTP process start.

- The clinical site investigator or pharmacist will have to inform Marken at least 72 hours before the pick-up time.
- Marken will send the shipping material to the site on the day before the pick-up time at the latest.
- Marken will deliver the IMP at patients' home at Visit 2, Visit 6, Visit 8, and Visit 10.

8.1.4 Route and method of investigational medicinal product administration

Toujeo will be self-administered once daily by SC injection, in the left or right anterolateral or left or right posterolateral abdominal wall or thighs or upper arms. Within a given area, location of the injection site of IMP should be changed (rotated) at each time to prevent injection site skin reactions.

The injection sites for IMP and NIMP should be different so that, if any, an injection site reactions can be attributed specifically either to IMP (Toujeo) or NIMP (mealtime insulin).

8.1.5 Starting dose of investigational medicinal product

After randomization, patients will follow the investigator's instruction to start the IMP (Toujeo) and the daily dose of Toujeo at Visit 2-Step 2.

Patients randomized in the virtual group will receive the IMP by DTP process ([Section 8.1.3](#)) while patients in the traditional group will receive their IMP at the site at Visit 2-Step 2. The IMP should **NOT** be started until the completion of all the baseline performances (see flowchart in [Section 1.2](#)) and discussed with the investigator at Visit 2-Step 2, which should occur 7 (\pm 4) days after the randomization interactive response technology (IRT) call.

The starting dose of IMP on Day 1 is the patient's current insulin glargine 100 U/mL dose, ie, the same dose used on the day before. Patient should administer Toujeo at the same time of the day as their previous insulin glargine 100 U/mL injection, which is usually in the morning or in the evening around the same time daily.

Patient should not change the injection time during the 24-week treatment period.

The date, time, and dose of Toujeo will be documented in the e-CRF.

8.1.6 Adjustment of investigational medicinal product

Investigators should follow Toujeo prescribing information to adjust Toujeo (9) dose. It is expected that a higher dose of Toujeo is needed to maintain the same level of glycemic control, when patients shift the basal insulin from insulin glargine 100 U/mL (eg, Lantus or Basaglar) to Toujeo. During the treatment period, Toujeo will be titrated at the investigator's discretion to achieve the fasting glycemic target while avoiding hypoglycemia.

The target range for fasting (prebreakfast/preinjection) plasma glucose is between 80 and 130 mg/dL (4.4 and 7.2 mmol/L).

The upward dose titration should continue until the patient reaches the target fasting (prebreakfast/preinjection) SMPG. All efforts should be made to reach the target ranges for plasma glucose by 6 to 8 weeks post randomization. Thereafter, the dose will be adjusted as necessary to maintain the glycemic control until the end of treatment (EOT) at Week 24.

Changes in the Toujeo dose are based on the average fasting pre-breakfast SMPG values of past 3 days measured by the patients. If the fasting SMPG is ≥ 130 mg (7.2 mmol/L), the Toujeo dose will be increased by 10%. [Table 1](#) provides examples for the 10% titration rule. Other preprandial (prelunch, predinner) SMPG measurements may also be taken into account.

If considered helpful to achieve the fasting glycemic target by the investigator, the mealtime insulin (including bedtime) may be titrated before additional basal insulin titration to achieve a bedtime and prebreakfast glucose delta < 50 mg/dL.

A dose increase may be split into 1-2 incremental dose steps rather than implementing the entire dose increase at once, if it is considered by the investigators or medically qualified designee to be in the best interest of the patient to do so. The dose of Toujeo should be titrated no more frequently than every 3 to 4 days.

Table 1 – Titration of investigational medicinal product dose

Toujeo daily dose	10% increase rules
Up to 21 u	2 u , or split into 2 x 1 u over 3 days apart
22 to 29 u	2 or 3 u , split into 2 or 3 x 1 u over 3 days apart
30 to 36 u	3 u, split into 3 x 1 u over 3 days apart
37 to 44	3 or 4 u, split into 2 x 2 u over 3-4 days apart
≥45 u	4 u , split into 2 x 2 u over 3-4 days apart

Good clinical judgment is to be exercised while titrating the basal insulin dose.

Regular SMPG is very important in order to achieve the blood glucose targets. It is recommended to perform daily fasting/prebreakfast SMPG and 5-point profiles to support the titration process. More frequent SMPG at other timepoints (eg, postbreakfast and postdinner) may be needed at the investigator’s discretion.

Patients will be familiarized with the adjustment schedule so that they will be able to monitor the dose adjustment with the assistance of the investigator or medically qualified designee. During the first month of the treatment period, weekly contacts between the investigator and patient are scheduled to assess the response to treatment and to decide on dose adjustment. During these visits (phone or virtual), patients will report their SMPG data, insulin doses and hypoglycemia to the study site.

It is at the discretion of the investigator to allow well-trained patients to adjust their IMP insulin dose between the scheduled visits without prior consultation of the site personnel.

In cases of hypoglycemia, dose will be adjusted as follows:

- Upward titration is to be stopped for 1 week after a case of severe hypoglycemia (requiring assistance) or ≥ 2 episodes of documented symptomatic hypoglycemia within a week, unless there was a manageable factor (eg, omission of a meal or overdosed insulin) for the event
- Doses of basal insulin or meal-time insulin may be reduced or modified at any time for hypoglycemia during the study
- Patients who experience mild to moderate hypoglycemia as a result of a missed meal, unusual exercise, or alcohol use will be counseled on the correction of those behaviors and should not reduce their insulin dose

8.1.7 Evaluation of patients not meeting glycemic targets

In case the target fasting glycemic goal cannot be achieved in spite of successive IMP dose titration over 4-8 weeks, the investigator should ensure that no reasonable explanation exists for insufficient glucose control and in particular that:

- Plasma glucose was actually measured in fasting condition (eg, before breakfast within 30 minutes window prior to injection)

- IMP and mealtime insulin are properly injected
- There is no intercurrent disease which may jeopardize glycemic control (eg, infectious disease)
- Compliance to diet and lifestyle is appropriate

If any of the above can reasonably explain the insufficient glycemic control, the investigator should take appropriate action, eg:

- Adjust the IMP dose and mealtime insulin dose
- Check the compliance of IMP and mealtime insulin injection
- Evaluate and treat any intercurrent disease (to be reported in the AE/SAE/concomitant medication parts of the e-CRF)
- Organize a specific interview with a registered dietician or other medically qualified person to discuss with the patients on the absolute need to be compliant to diet and lifestyle recommendations

8.2 NONINVESTIGATIONAL MEDICINAL PRODUCT(S)

The noninvestigational medicinal products (NIMP) are the protocol-mandated mealtime insulins, ie, rapid insulin analogs (Humalog, Novolog, or Apidra), which have been used by the patient before the screening visit. This background treatment will not be supplied by the sponsor.

The patients in both study groups will continue with their existing mealtime insulin throughout the study. The type of mealtime rapid-insulin analog for each patient cannot be changed during the course of study. Any other types of meal-time insulin are prohibited for this study.

The injection sites should be different for the fast-acting mealtime insulin analogs from the IMP so that any injection site reactions can be attributed specifically either to the fast-acting insulin or to IMP. Changes in the body areas used for injection of either insulin should be avoided as far as possible during the study.

8.2.1 Adjustment of noninvestigational medicinal products

The dose of the mealtime insulin analogs (Humalog, Novolog, or Apidra) will be titrated to achieve a target of 2-hour postprandial plasma glucose. The dose adjustment is at the investigator's discretion in accordance with the national product label. Two recommended dose titration algorithms are based on a pattern of postprandial plasma glucose results of SMPG (simple titration) OR based on the carbohydrate content of the meal (carb counting).

- The titration goal is a 2-hour postprandial SMPG in the range of 130 and 180 mg/dL (7.2-10.0 mmol/L) while avoiding hypoglycemia. For the purpose of this protocol, 2-hour postprandial is defined as 2 hours after the start of the meal.
- While basal insulin doses are increased, mealtime insulin doses may be reduced to avoid daytime hypoglycemia as deemed appropriate by the investigator.

- Appropriate adjustment in mealtime insulin will continue throughout the entire treatment period (Week 0-24).

The two recommended regimens are described in [Table 2](#) and [Table 3](#).

Table 2 - Simple titration: Titration of mealtime insulin based on a pattern of post-meal glucose (median <130/>180 mg/dL in the prior 3 days)

Mealtime dose of Insulin	Pattern of postprandial BG values <130 mg/dL ^a	Postprandial BG values >180 mg/dL ^a
≤10 U	Decrease dose by 1 U	Increase dose by 1 U
11-19 U	Decrease dose by 2 U	Increase dose by 2 U
≥20 U	Decrease dose by 3 U	Increase dose by 3 U

^a If more than 50% of the mealtime blood glucose (2-hour PPG) values for the week were above target.

Table 3 - Carbohydrate counting: Insulin-to-carbohydrate ratio group

Mealtime dose of Insulin	Pattern of postprandial BG values <130 mg/dL ^a	Postprandial BG values >180 mg/dL ^a
1 U/20 g	Decrease to 1 U/25 g	Increase to 1 U/15 g
1 U/15 g	Decrease to 1 U/20 g	Increase to 1 U/10 g
1 U/10 g	Decrease to 1 U/15 g	Increase to 2 U/15 g
2 U/15 g	Decrease to 1 U/10 g	Increase to 3 U/15 g
3 U/15 g	Decrease to 2U/15 g	Increase to 4 U/15 g

^a If more than one-half of the mealtime blood glucose values for the prior 3 days were above target.

Starting recommendation 1 U to 15 grams carbs

Consider calculating insulin to carb (I:C) ratio = 500/total daily dose (TDD) of insulin.

Investigators will also be provided with an initial guideline of 1800/TDD as a correction factor to be used if applicable at the investigators' discretion.

The injection of the mealtime insulin analogs in relation to the meal intake will be done according to the individual habits of the patient prior to the study while following the instructions in the national product label.

Dietary modifications (eg, snacks) will be made by the Investigator, dietician, or other medically qualified person based on his/her best judgment.

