
STUDY TREATMENTS
 
Investigational medicinal product
 
Formulation:
 
Route of administration:
	
Toujeo (insulin glargine 300 U/mL, HOE901-U300)
 
Toujeo (insulin glargine-U300) will be supplied as a sterile, nonpyrogenic, clear, colorless solution in the Toujeo SoloStar® prefilled (disposable) pen (insulin glargine 300 units/mL solution for subcutaneous [SC] injection).
 
Each Toujeo SoloStar contains in total 450 units of insulin glargine (1.5 mL of 300 units/mL insulin glargine solution). This pen allows dose setting in the range of 1 to 80 units with a minimum of 1 unit increment.
 
Dilution or mixing of Toujeo with other insulin products is not allowed.
 
Subcutaneous injection once daily (self-administration)

Dose regimen:
 
Noninvestigational medicinal products
 
Formulation:
 
Route(s) of administration:
 
Dose regimen:
	
Starting dose of Toujeo is the patient's existing insulin glargine 100 U/mL dose prior to Day 1. Toujeo will be titrated based on self-measured, fasting (prebreakfast/preinjection) plasma glucose levels (target range 80 to 130 mg/dL; 4.4 to 7.2 mmol/L) while avoiding hypoglycemia.
 
Patients in both treatment groups will continue with their existing rapid-acting mealtime insulin analogs (Humalog, Novolog, or Apidra) during the study.
 
Solution for SC injection
 
Subcutaneous injection
 
Dosing of the rapid-acting mealtime insulin will be adjusted based on the pattern of mean postmeal SMPG level or based on the carbohydrate content of the meal (carb counting) as per instruction of the investigator; target range for 2-hour postprandial plasma glucose is 130 to 180 mg/dL (7.2 to 10.0 mmol/L).

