- After all baseline assessments have been completed, the investigator will instruct patients to initiate the first dose of the IMP, Toujeo basal insulin, and patients will document the dose and date/time in the eDiary.

All patients in both study groups will be reminded by the study staff to refer to the instructions for use to properly use the Toujeo pens. IMP administration will be explained to patients including reminding the IMP dose, time of the once daily administration, and dose titration requirements ([Section 8.1](#)).

The day of the first administration of IMP will be defined as Day 1.

All patients are asked to self-titrate their IMP according to the algorithm provided ([Section 8.1](#)). The short-acting insulin analog will be continued for mealtime insulin requirements and correction of SMPG according to recommendation ([Section 8.2.1](#)). Investigators and their study staff are required to offer adequate training, thus enabling patients to successfully self-titrate their insulins.

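### In Tables 2 and 3 of Protocol 8.2.1 the mealtime dose-decrease column carries an above-target footnote, and Table 2 gives two different look-back periods

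*Protocol*

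**What the plan says.** Protocol 8.2.1 sets the target: "The titration goal is a 2-hour postprandial SMPG in the range of 130 and 180 mg/dL". It then recommends two schemes, simple titration (Table 2) and carbohydrate counting (Table 3). Each table has a decrease column headed by values <130 mg/dL and an increase column headed by values >180 mg/dL. Marker a stands on both headers in both tables.

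- Table 2, title: "Titration of mealtime insulin based on a pattern of post-meal glucose (median <130/>180 mg/dL in the prior 3 days".
- Table 2, footnote a: "If more than 50% of the mealtime blood glucose (2-hour PPG) values for the week were above target".
- Table 3, footnote a: "If more than one-half of the mealtime blood glucose values for the prior 3 days were above target".
- Synopsis, dose regimen for the noninvestigational products: "Dosing of the rapid-acting mealtime insulin will be adjusted based on the pattern of mean postmeal SMPG level", with no look-back.

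The text of 8.2.1 leaves the adjustment to the investigator's discretion, within the national label. Protocol 10.1.2.2 refers back to 8.2.1 for mealtime insulin and asks sites to give training, "enabling patients to successfully self-titrate their insulins".

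**The concern.** Both footnotes describe only readings that are too high, which is the right condition for raising a dose and the wrong one for lowering it. Neither footnote states a below-target condition, yet between them they cover 8 decrease rows (3 in Table 2, 5 in Table 3). A site that teaches from the tables finds a header telling it to reduce rapid-acting insulin and a footnote that is not met when readings are low.

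The second problem is inside Table 2. The title looks back 3 days and the footnote looks back a week, and nothing says which governs or how they combine.

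What is at stake is clear dosing instructions for a drug that can cause hypoglycemia. These are the only mealtime algorithms in the protocol.

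**Working it through.** The plan states no figure to reproduce here. The check is one of logic, with glucose values in mg/dL assumed for illustration.

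**1. Footnote against header.** Inputs: target 130 to 180 (8.2.1), decrease header <130, and footnote a requiring more than half of values above target, that is >180.

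Assumed values 110, 120, 125:
- median = 120, which is below 130;
- values below 130: 3 of 3, so the header calls for a decrease;
- values above 180: 0 of 3, so footnote a is not met.

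This is general. If the median of a set of readings is below 130, at least half of the readings are below 130. At most half can then be above 180, so more than half cannot be. A simulation of 200,000 sets at each of n = 3, 5, 7, 9 and 21 found no set meeting both conditions. The result applies when header and footnote are read on the same readings.

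**2. Three days against a week (Table 2).** Assumed daily post-meal values, oldest first: 190, 185, 195, 190, 120, 125, 115.
- Title rule, last 3 days (120, 125, 115): median = 120, a decrease.
- Footnote rule, whole week: 4 of 7 above 180 = 57%, an increase.

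The conflict does not need daily testing. Protocol 9.2.2.2.2 (Table 5) recommends 5-point profiles, with one post-meal value each, on 5 days a week. Remove the day 4 and day 7 values from the example:
- last 3 days (120, 125): median = (120 + 125)/2 = 122.5, a decrease;
- week: 3 of 5 above 180 = 60%, an increase.

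For a sense of how sensitive the trigger is, independent normal readings were simulated with true mean 150 to 190, SD 40 to 60 and 1 or 3 post-meal values a day. None of these settings comes from the documents. The 3-day median and the 7-day majority rule disagreed on an increase in about 3% to 27% of cases, and in about 21% to 27% when the true mean was within 10 mg/dL of 180. This does not estimate how often it would happen in the trial.

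**3. Median against mean (Table 2 title against synopsis).** Assumed values 100, 125, 190:
- median = 125, a decrease;
- mean = (100 + 125 + 190)/3 = 415/3 = 138.3, in target, no change.

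**The case against.** The strongest reply is that no competent site would be misled. The headers and the cells beneath them show the direction, and the schemes are recommendations. The protocol also provides other routes to a lower dose. Section 8.1.6 says "Doses of basal insulin or meal-time insulin may be reduced or modified at any time for hypoglycemia during the study", and 8.2.1 adds that, while basal doses are rising, "mealtime insulin doses may be reduced to avoid daytime hypoglycemia as deemed appropriate by the investigator". Investigators review glucose records and instruct patients on doses (9.2.2.2.2, 10.1.3). All of this stands and keeps the point minor. It does not supply the missing condition or settle the look-back.

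A reader might infer several stronger things that the documents do not support:

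- *The protocol has no below-target trigger, so a literal reader would hold the dose.* Table 2's title gives one (median <130), and both headers repeat the threshold. The reader meets a contradiction, not an instruction to hold. The defect is plainer in Table 3, where only the header opposes the footnote.
- *Patients adjust mealtime insulin unsupervised from these tables.* In 10.1.2.2 the explicit self-titration instruction concerns Toujeo. The training sentence covers insulins generally, but mealtime changes follow the investigator's instructions.
- *The median and majority wordings are themselves in serious conflict.* On one window with an odd number of values they agree. The protocol contains no majority-below-130 rule, so such a rule cannot be set against the title as a second protocol statement.
- *The synopsis creates a third operative rule.* It is a summary phrase with no window or dose step; 8.2.1 is the operative text.

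The window conflict also vanishes for a patient whose only post-meal readings that week fall in the last 3 days.

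**Conclusion.** The point holds as a minor inconsistency in the operative dosing text. In both tables footnote a contradicts the decrease header it is attached to, and in Table 2 it also contradicts the title. Eight decrease rows are affected. Separately, Table 2's two look-backs can call for opposite dose changes on plausible readings.

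The footnote contradiction follows from the wording and rests on no assumed data; the examples only illustrate it. The look-back examples show that the rules can conflict, not how often they would. The same marker placement recurs in two tables with differently worded footnotes, so an error in reading the PDF is unlikely.

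Nothing here supports a claim of bias between arms or of harm. Both groups use the same tables, and sample size and analysis do not depend on them. SAP section 2 records early termination with 15 patients randomized, so the correction now matters mainly for the record and for reuse; Protocol section 4 describes the study as a pilot ahead of full-scale studies.

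**What to change.** 1. In both tables, give the decrease column its own footnote: *if more than half of the 2-hour postprandial values in the look-back period were below target (<130 mg/dL)*. Keep *above target (>180 mg/dL)* for the increase column only.
2. In Table 2, state one look-back in the title and the footnote. The prior 3 days would match the present title and Table 3. The window, and whether to keep the median in the title beside a majority rule in the footnote, are clinical choices for the clinical team to confirm.
3. Align the word *mean* in the synopsis with 8.2.1. This is editorial.

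The cost is one sentence per table and a few words elsewhere, with no change to visits, data collection, sample size or analysis. Correcting the direction of the footnote is a clarification. Fixing the window touches an insulin dosing trigger, so under Protocol section 15 it may count as an amendment needing IRB/IEC approval and not as a purely administrative change.
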